6.6 Number of study-related post-operative visits unrelated to standard of care

All unscheduled visits with “Non-Standard of Care” checked will be considered study related post-operative visits unrelated to standard of care. The number of study-related post-operative visits unrelated to standard of care of each subject will be presented for the whole follow up period (post-op to end of study) and by time intervals (post OP – 1 month/ > 1 month – 3 months/ > 3 months – 6 months/ > 6 months – 12 months/ > 12 months – 18 months/ > 18 months – 24 months/ > 24 months (if any)).

6.7 Incidence of Seroma

Seroma will be identified from AE. A frequency table for seroma for the whole follow up period (post-op to end of study) and by time intervals (post OP – 1 month/ > 1 month – 3 months/ > 3 months – 6 months/ > 6 months – 12 months/ > 12 months – 18 months/ > 18 months – 24 months/ > 24 months (if any)) will be presented.

7 Statistical Analyses of Other Endpoints

7.1 Subjects Dispositions

The summary of the number of subjects enrolled (intent to treat (ITT)), treated with Phasix™ Mesh (mITT), completed the study, and discontinued from the study (by reason of discontinuation) will be provided. Screen failures will be summarized for inclusion/exclusion criteria that were not met.

7.2 Protocol Deviations

The number of subjects with protocol deviations will be summarized with descriptive statistics by nature of the deviation. Protocol deviations will be listed with date of occurrence and the nature of deviation.

7.3 Demography and Background Disease Characteristics

Demographics and background disease characteristics will be summarized with descriptive statistics using the mITT analysis set. Summary statistics for categorical variables will include frequency counts and percentages and for continuous variables will include mean, standard deviation, minimum, median, and maximum.

Demographics and baseline characteristics variables include:

- Age at screening (year)
- Sex (Male, Female)
- Race (American Indian or Alaskan Native, Asian, Black or African American, Native Hawaiian or Other Pacific Islander, White and Other)
- Ethnicity (Hispanic/Latino)
- Baseline Weight
- Baseline Height
- Baseline Body Mass Index (BMI) calculated from weight and height.

Weight change over time and BMI change over time will be summarized by visit.

Background disease characteristics including medical history (in 5 categories: cardiac disease, respiratory illness, renal disease, vascular disease and other; and in sub-terms) and hernia assessment will be summarized.

7.4 Prior/concomitant medication

All current pain medication is captured at baseline. Hernia associated pain medication is captured at 12 and 24 months.

A frequency table by Baseline, Month 12 and Month 24 visit will be presented showing the intake of prescription or OTC medications including the classification in “non-narcotic” and “narcotic”.

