#### 6.1.8 Concomitant Pain Medication Usage

Prescription and over the counter (OTC) pain medication must be recorded in the source documentation and in the eCRF. The condition/s necessitating the pain medication will be recorded. All current pain medication will be captured at baseline, 12 months, and 24 months.

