### 6.3.3 Assessments

Subjects should report to their respective study site for follow-up visits at the following times:

- 1 month assessment: Day  $30 \pm 7$  days post device placement
- 3 month assessment: Day  $90 \pm 30$  days post device placement
- 6 month assessment: Day  $180 \pm 30$  days post device placement
- 12 month assessment: Day  $365 \pm 30$  days post device placement
- 18 month assessment: Day  $545 \pm 30$  days post device placement
- 24 month assessment: Day  $730 \pm 30$  days post device placement

At each study visit, the following procedures will be completed and these data recorded in source documentation and on the eCRF:

- Physical exam to check for hernia recurrence and surgical complications.  
Note: If the subject undergoes imaging for any reason and a recurrent hernia is identified, it must be recorded.
- Carolinas Comfort Scale®
- SF-12®
- Concomitant pain medication usage (all pain medication will be captured at baseline. Hernia associated pain medication only will be captured at 12 and 24 months)
- Assessment of AEs/complications

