#### 6.4 TABLE OF STUDY EVENTS

Study Procedure	Screening and Baseline Period	Surgery	1 Month Visit	3 Month Visit	6 Month Visit	12 Month Visit	18 Month Visit	24 Month Visit	Unscheduled Visit/Early Termination
Visit Window (days)	Within 60 days of consent	0	30 $\pm$ 7	90 $\pm$ 30	180 $\pm$ 30	365 $\pm$ 30	545 $\pm$ 30	730 $\pm$ 30	--
Describe study to potential subject	X								
Obtain informed consent	X								
Verify eligibility criteria	X	X							
Collect demographics and medical history	X								
Conduct physical examination	X		X	X	X	X	X	X	X
Placement Procedure of Device		X 							
Carolinas Comfort Scale®	X		X	X	X	X	X	X	X
SF-12®	X		X	X	X	X	X	X	X
Collect adverse events/ complications		X	X	X	X	X	X	X	X
Collect pain medication usage	X					X		X	

 See Section 6.2 for surgical procedure details

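### SAP 7.4 tabulates all analgesics at baseline beside hernia-associated analgesics only at months 12 and 24, so the columns are not comparable and may show a spurious fall in use

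*SAP*

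**What the plan says.** SAP 7.4 gives the scope of collection in two sentences: "All current pain medication is captured at baseline. Hernia associated pain medication is captured at 12 and 24 months". The next sentence specifies the output: "A frequency table by Baseline, Month 12 and Month 24 visit will be presented", covering prescription and over-the-counter drugs and classed as narcotic or non-narcotic. The section has no split by indication, no baseline column limited to hernia-associated use, and no caution about comparing visits.

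The protocol gives two different rules. Section 6.1.8 says "All current pain medication will be captured at baseline, 12 months, and 24 months". Section 6.3.3 says "Hernia associated pain medication only will be captured at 12 and 24 months", which is the rule the SAP adopts. The schedule in Protocol 6.4 says only "Collect pain medication usage", at baseline, 12 and 24 months, and SAP Table 1 repeats that row. Neither schedule states a scope.

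Protocol 6.1.8 also says "The condition/s necessitating the pain medication will be recorded".

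**The concern.** Under the SAP's rule, the medication eligible to be counted at months 12 and 24 is a subset of what is eligible at baseline. The three columns would sit side by side under one description while measuring different things. Long-term analgesia for an unrelated condition would be visible before surgery and invisible afterwards.

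The study is single-arm, so no comparison group would show the same artificial drop. The direction matters too. The protocol's background names discomfort and chronic pain among the complications of non-absorbable mesh, so a reader could easily take lower analgesic or narcotic use after a resorbable mesh as a benefit.

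The conflict between Protocol 6.1.8 and 6.3.3 adds a second uncertainty. Sites could have followed either rule, and follow-up scope might differ between sites.

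**Working it through.** The plan states no analgesic rate, test or sample-size figure on this point, so there is nothing to reproduce. The check compares the texts and then works out what the mismatch does if nobody's medication changes.

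**Scope by source**

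| Source | Baseline | Months 12 and 24 |
|---|---|---|
| SAP 7.4 | all current | hernia-associated |
| Protocol 6.3.3 | all | hernia-associated only |
| Protocol 6.1.8 | all current | all current |
| Protocol 6.4 and SAP Table 1 | not stated | not stated |

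Two sources agree on a scope that changes between visits, one contradicts them, and the schedules are silent.

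**Inputs**

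- N = 30 at every visit. The documents say up to 30 subjects (Protocol 5.1 and 7.2, SAP 3.2). Full enrolment and no dropout are assumptions.
- e = number of subjects whose baseline analgesic use is exclusively for non-hernia conditions. The documents do not give it.
- No true change in anyone's medication (assumption, to isolate the artefact).

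**Formula.** Apparent fall = e/N. For illustration, assume 15 of 30 subjects use an analgesic at baseline (50%):

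| e | Users shown at follow-up | Apparent fall |
|---|---|---|
| 0 | 15/30 = 50% | 0 points |
| 1 | 14/30 = 46.7% | 1/30 = 3.3 points |
| 3 | 12/30 = 40% | 3/30 = 10 points |
| 9 | 6/30 = 20% | 9/30 = 30 points |

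**The same result in proportions.** Let p be the share of subjects on any analgesic and h the share of those users with at least one hernia-associated analgesic. Then the apparent fall is p(1 − h). Over assumed ranges of p = 0.3 to 0.6 and h = 0.25 to 0.75:

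- smallest: 0.3 × (1 − 0.75) = 0.075, or 7.5 points
- middle case, p = 0.4 and h = 0.5: 12/30 (40%) at baseline and 6/30 (20%) later, or 20 points
- largest: 0.6 × (1 − 0.25) = 0.45, or 45 points

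If h = 1 the fall is zero, which matches e = 0.

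**The narcotic row.** The same arithmetic applies to each class separately. Take a subject with a narcotic for another condition and a non-narcotic for the hernia. That subject remains a user overall (change 0) but leaves the narcotic row (change 1/30 = 3.3 points).

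**With one definition throughout.** If baseline is also limited to hernia-associated use, the artefactual fall is 0 under the same no-change assumption.

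**The case against.** The strongest reply is that SAP 7.4 discloses both scopes immediately above the table and plans no comparison. Where this SAP wants change it says so: absolute change from baseline for the Carolinas Comfort Scale and SF-12 (6.2), weight and BMI change (7.3), and shift in wound classification (7.8.4). Section 7.4 has no such wording, and it falls under other endpoints in a study without a formal hypothesis. The SAP text contains no output shells for any table, so a missing column label in 7.4 does not show that the output will be unlabelled. The artefact is also conditional. If sites collected everything, as Protocol 6.1.8 says, and all records are tabulated, it does not arise. The illustrative percentages rest on assumed inputs.

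Much of this stands, and it limits the weight of the point. No test or change score is affected, and the size is unknown and may be zero. It does not remove the problem. Scopes stated in SAP prose do not automatically reach the reader of the table, and a layout by visit starting at baseline invites a before-and-after reading. The SAP does guard against this elsewhere: in 6.2 it limits change in mesh sensation and in the total score to subjects who had mesh at baseline. If sites did follow 6.1.8, SAP 7.4 misdescribes its own data, so the text needs correcting either way.

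It is also fair to say that classifying baseline records afterwards will not match a restriction applied at capture exactly. That leaves a smaller mismatch than the present one.

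**Conclusion.** The concern holds. Followed as written, SAP 7.4 compares a wider definition at baseline with a narrower one at months 12 and 24, and the mismatch can only push towards less apparent use. With 30 subjects per visit, each subject with exclusively non-hernia use costs 3.3 points, overall or within the narcotic row. The total cannot be determined from the documents.

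The textual conflict is certain. An actual artefact depends on sites having applied the hernia-only rule at follow-up and on at least one such subject. Because pain medication is neither a primary nor a secondary endpoint, this should be corrected before the table is produced, but it does not threaten the study's main results.

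**What to change.** In SAP 7.4:

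1. Show baseline use restricted to hernia-associated medication, by the recorded condition, beside months 12 and 24. Report all-medication baseline use separately as a baseline characteristic, with no change interpretation.
2. State the classification rule before the table is run. One example: a baseline record is hernia-associated if any of its recorded conditions is the study hernia or pain at its site.
3. If sites recorded all pain medication at months 12 and 24, tabulate both definitions at all three visits.
4. If the condition is not available in the eCRF, label each column with its scope and state that the columns do not support a change from baseline.

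Reconcile Protocol 6.1.8 with 6.3.3 and SAP 7.4, and confirm from the eCRF what was collected at follow-up.

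The cost is SAP wording plus classification of baseline records for at most 30 subjects. That depends on where the condition is held. Protocol 6.1.8 says "pain medication must be recorded in the source documentation and in the eCRF" but does not say whether the condition is in the eCRF as well. The fallback in item 4 costs one footnote. If sites did not collect non-hernia medication at months 12 and 24, it cannot be recovered in the analysis.

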7.5 Follow-up Period

The duration of follow-up period after the surgery during the study is calculated as:

 Last day in study – date of the surgery.

Last day in study is defined as latest of: discontinuation/completion day, last visit day, last event occurrence day.

The hospital duration after the surgery during the study is calculated as:

 Date of the discharge – date of the surgery.

7.6 Intra-operative characteristics

The procedural overview and surgical details data will be summarized by subject with descriptive statistics; the drain data will be summarized by drain.

7.7 Device failure, malfunctions and defects

The investigator records if the surgical mesh device used in the study procedure failed to meet its performance specifications whether due to mechanical failure, malfunction or defects. Device failures, malfunctions or defects will be tabulated by the failure code.

7.8 Safety Endpoints

7.8.1 Adverse Event

Adverse events will be collected from the time of enrollment through the end of study participation (either study completion or early discontinuation) and will be documented on the medical record or source document and on study eCRFs. Events with an onset prior to enrollment should be reported in the subject's medical history. AEs will be coded using MedDRA version 16.1. AEs will be summarized by system organ class and preferred term.

The number and percentage of subjects with at least one AE, total number of AEs, AEs by relationship to the device/procedure, AEs by severity of the event, and serious AE will be summarized.

Listing of all AEs, as well as all SAEs will be provided.

7.8.2 Mesh Infection

A frequency table for Mesh Infection for the whole follow up period (post-op to end of study) and by time intervals (post OP – 1 month/ > 1 month – 3 months/ > 3 months – 6 months/ > 6 months – 12 months/ > 12 months – 18 months/ > 18 months – 24 months/ > 24 months (if any)) presenting the number of events and number of subjects with events will be displayed.

7.8.3 Surgical Site Infection

Surgical site infection is collected per Center for Disease Control and Prevention (CDC) ("Guideline for Prevention of Surgical Site Infection, 1999").

A frequency table for Surgical Site Infection for the whole follow up period (post-op to end of study) and by time intervals (post OP – 1 month/ > 1 month – 3 months/ > 3 months – 6 months/ > 6 months – 12 months/ > 12 months – 18 months/ > 18 months – 24 months/ > 24 months (if any)) presenting the number of events and number of subjects with events will be displayed.

7.8.4 CDC Wound Classification

Wound Classification is collected per Center for Disease Control and Prevention (CDC) ("Guideline for Prevention of Surgical Site Infection, 1999").

Wound Classification will be summarized at baseline, pre-operative and post-operative and shift from previous visit will be presented.

7.8.5 Reoperation

The re-operation will be summarized by subject and by reoperation with descriptive statistics; the drain data will be summarized by drains, if applicable.
